10 STUDY OVERSIGHT

The principal investigators will be responsible for study oversight, including monitoring safety, ensuring that the study is conducted according to the protocol and ensuring data integrity. The PIs will review the data for safety concerns and data trends at regular intervals, and will report Unanticipated Problems (UPs), protocol deviations, or any other significant events that arise during the conduct of the study to the IRB, NIDCR, and Data and Safety Monitoring Board (DSMB) in accordance with their prescribed timelines.

In addition to the PIs' responsibility for oversight, study oversight will be under the direction of a DSMB composed of members with appropriate clinical, statistical, scientific, and ethical expertise. The NIDCR will appoint the Board. The DSMB will meet annually to assess safety and efficacy data, study progress, and data integrity for the

study. If concerns arise, more frequent meetings may be held. The DSMB will operate under the rules of an NIDCR-approved charter that will be approved at the organizational meeting of the DSMB. The DSMB will provide recommendations to the NIDCR.

11 CLINICAL SITE MONITORING

Clinical site monitoring is conducted to ensure that the rights of human subjects are protected, that the study is implemented in accordance with the protocol and/or other operating procedures, and that the quality and integrity of study data and data collection methods are maintained. Monitoring for this study will be performed by NIDCR's Clinical Research Operations and Management Support (CROMS) contractor. The monitor will evaluate study processes and documentation based on NIDCR standards and the International Conference on Harmonisation (ICH), E6: Good Clinical Practice guidelines (GCP).

Details of clinical site monitoring will be documented in a Clinical Monitoring Plan (CMP) developed by the CROMS contractor, in collaboration with the NIDCR Office of Clinical Trials and Operations Management (OCTOM) and the NIDCR Program Official/Project Scientist. The CMP will specify the frequency of monitoring, monitoring procedures, the level of clinical site monitoring activities (e.g., the percentage of subject data to be reviewed), and the distribution of monitoring reports. Some monitoring activities may be performed remotely, while others will take place at the study site(s). Staff from the CROMS contractor will conduct monitoring activities and provide reports of the findings and associated action items in accordance with the details described in the CMP. Documentation of monitoring activities and findings will be provided to the site study team, the study PIs, OCTOM, and the NIDCR. The NIDCR reserves the right to conduct independent audits as necessary.

12 STATISTICAL CONSIDERATIONS

Statistical Design, Power, and Statistical Analysis Plan:

12.1 Study Hypotheses

Primary Null Hypothesis H0: No difference between intervention and control group participants in mean number of qualifying half-day toothbrushing episodes per week, through Month 6 visit.

[figure not shown]
Primary Alternate Hypothesis HA: Intervention and control group participants differ in mean number of qualifying half-day toothbrushing episodes in per week, through the Month 6 visit.

Secondary hypotheses relate to differences between intervention and control group participants in the secondary outcomes. (See Sections 3.1.2 and 3.2.2.)

Secondary hypotheses also relate to behavioral economic measures mediating the relationship between the intervention and toothbrushing. (See Sections 2.2 & 12.4.)

12.2 Sample Size Considerations

With 2 parallel groups, the sample size calculation was conservatively conducted for one continuous outcome using short-term pilot data; the mean number of qualifying brushing episodes in a half-day window per week through 6 weeks was 5.5 with a standard deviation (SD) of 4.8 for a coefficient of variation (CV) of 0.87. To be more conservative, a SD 25% larger (i.e. 6.0) was used. The mean percent of qualifying brushing episodes (out of 14 half-days per week) was 63% with a SD=32% for a CV=0.514. A sample size of 91 in each group is estimated to have 84% power to detect a difference in means of 2.65 with a common SD of 6.0 using a two group t-test with 2-sided alpha=0.05.

In addition, a sample size of 91 in each group was estimated to have 85% power to detect a 1.25-fold change in means (expected ratio) between intervention and control with the larger (more conservative) CV=0.525 using a two group 2-sided t-test with alpha=0.05. With a CV=0.567 and a 1.25-fold change or a CV=0.695 and a 1.30-fold change, n=91 per group is still estimated to have 80% power.

Assuming 75% retention over 12 months, a total of 244 parent-child dyads (N=488) will need to be enrolled. (Retention was 85% over 24 months in the team's recently completed glass ionomer sealant and fluoride varnish trial (GIFT) in a similar

population. Retention was 75% over 2 months in the BEECON pilot trial, but retention procedures have been added including a 2 week run-in to eliminate people enrolling only for the powered toothbrush.)

Sample sizes for semi-structured interviews and focus group discussions are based on prior experience. Focus group discussions with a total of 40 parent/caregiver participants are expected to reach saturation, but it is possible an additional focus group discussion will be needed to reach saturation.

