3.2 Study Outcome Measures

3.2.1 Primary

The primary outcome is toothbrushing performance through the Month 6 visit, measured with a Bluetooth-enabled toothbrush, and expressed as a mean of the number of qualifying half-day toothbrushing episodes per week. A toothbrushing session recorded with the app qualifies to contribute to the weekly count if it lasts at least one minute and occurs within one of the 14 possible half-day windows during a week; only one session per half-day window contributes to the weekly count, which can range from 0 to 14.

A participant qualifies for weekly drawing eligibility as follows:

- Low threshold - if the child's teeth were brushed at least once per day for at least one minute each day of the week;
- High threshold - if the child's teeth were brushed at least once per half-day for at least one minute each day of the week.

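### Section 12.2's two pilot summaries of weekly brushing (5.5 episodes, and 63% of 14 = 8.8) conflict, and its 85% power for a 1.25-fold change holds only for the second

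*Combined protocol and SAP*

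**What the plan says.** Section 3.2.1 defines the primary outcome as brushing through Month 6, "expressed as a mean of the number of qualifying half-day toothbrushing episodes per week", with a possible range of 0 to 14. The hypotheses in Section 12.1 use the same scale.

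Section 12.2 summarizes the pilot twice:

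- As a weekly count: the mean "through 6 weeks was 5.5 with a standard deviation (SD) of 4.8 for a coefficient of variation (CV) of 0.87".
- As a percentage: "The mean percent of qualifying brushing episodes (out of 14 half-days per week) was 63% with a SD=32% for a CV=0.514".

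Two power statements follow, both at 91 per group:

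- A difference in means of 2.65 has 84% power. The SD comes from the count: "To be more conservative, a SD 25% larger (i.e. 6.0) was used".
- As an addition, "a sample size of 91 in each group was estimated to have 85% power to detect a 1.25-fold change in means (expected ratio"), "with the larger (more conservative) CV=0.525 using a two group 2-sided t-test with alpha=0.05". A further sentence gives 80% power "With a CV=0.567 and a 1.25-fold change or a CV=0.695 and a 1.30-fold change".

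Enrolment is then set at 244 dyads, "Assuming 75% retention over 12 months". Section 12.4 analyses numeric outcomes with an identity link.

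**The concern.** A percentage of a fixed 14 half-days is the weekly count multiplied by 100/14. Rescaling by a constant leaves the CV unchanged, so two summaries of the same records must have the same CV and equivalent means. Here the CVs are 0.87 and 0.514, and the means are 39% and 63% of the maximum. As written, the two summaries conflict, and nothing in the documents explains the gap.

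The conflict matters because each power statement draws on a different summary. The difference calculation takes its SD from the count. The fold-change calculation uses a CV just above that of the percentage. All three CVs used for fold changes (0.525, 0.567, 0.695) lie below the count CV, so Section 12.2 gives no fold-change power for the summary whose wording matches the primary outcome.

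At stake is what the trial can be said to detect. A reader of a null result would take from Section 12.2 that a 25% gain had only a 15% chance of being missed. On the count summary, that chance is about half.

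**Working it through.** **Inputs (Section 12.2).** n = 91 per group; two-sided alpha 0.05; count mean 5.5, SD 4.8, CV 0.87; percent mean 63%, SD 32%, CV 0.514; inflated SD 6.0; ratio scenarios (CV, fold) of (0.525, 1.25), (0.567, 1.25) and (0.695, 1.30).

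**Method.** Two-group t-test, noncentral t with 2 × 91 − 2 = 180 degrees of freedom and noncentrality δ / (σ√(2/n)).

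- Difference scale: δ is the difference in episodes and σ is the SD.
- Ratio scale: δ = ln(ratio) and σ = √ln(1 + CV²). The plan does not name its ratio method. This log-normal form is inferred because it reproduces the plan's three ratio figures.

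**Step 1: the plan's own figures reproduce.**

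| Scenario | Stated | Recomputed |
|---|---|---|
| 2.65 episodes, SD 6.0 | 84% | 84.2% |
| 1.25-fold, CV 0.525 | 85% | 85.9% |
| 1.25-fold, CV 0.567 | 80% | 80.9% |
| 1.30-fold, CV 0.695 | 80% | 80.1% |

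For the second row: ln 1.25 = 0.2231; σ = √ln(1 + 0.525²) = 0.4934; noncentrality = 0.2231 / (0.4934 × √(2/91)) = 3.05. Enrolment also checks: 244/2 = 122 per group, and 122 × 0.75 = 91.5.

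**Step 2: the two summaries on one scale.**

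- Percent as episodes: 0.63 × 14 = 8.82; SD 0.32 × 14 = 4.48.
- Count as a share of 14: 5.5/14 = 39%.
- CVs: 4.8/5.5 = 0.87; 32/63 = 0.508, which agrees with the stated 0.514 within rounding of the inputs.
- The ratio CV is 0.525/0.514 = 1.02 times the percent CV, but 0.525/0.87 = 0.60 times the count CV.

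**Step 3: power for a 1.25-fold change under each summary, n = 91.**

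| Summary | Difference scale | Log-normal |
|---|---|---|
| Count: 0.25 × 5.5 = 1.375, SD 4.8; CV 0.87 | 48.5% | 51.4% |
| Count, SD 6.0 (6.0/5.5 = CV 1.09) | 33.7% | 39.4% |
| Percent: 0.25 × 8.82 = 2.205, SD 4.48; CV 0.525 for the log-normal | 91.0% | 85.9% |
| Percent with a 25% margin (SD 5.6; CV 0.6425) | 75.2% | 72.1% |

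For the first row, the noncentrality is 1.375 / (4.8 × √(2/91)) = 1.93 on the difference scale. On the log-normal scale it is 0.2231 / (0.7507 × √(2/91)) = 2.01. With all 122 per group retained, the first row becomes 60.6% and 63.8%.

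**Step 4: what is detectable with 80% power at n = 91.** On the count summary with SD 4.8, 2.00 episodes: (5.5 + 2.00)/5.5 = 1.36-fold (1.37-fold log-normal). A 1.25-fold change keeps 80% power only while the CV is at most 0.575 (log-normal).

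**Step 5: what 2.65 episodes means.** 2.65/5.5 = 48%; 2.65/8.82 = 30%.

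**The case against.** The strongest reply is that nothing is miscalculated and the sample size does not depend on the disputed statement. Both parts stand. The fold-change power is offered as an addition. The 84% calculation uses the count SD with a 25% margin, sits on the same scale as the identity-link analysis, and supports 91 per group without it.

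The phrase "with the larger (more conservative) CV=0.525 using a two group 2-sided t-test with alpha=0.05" also has a sensible referent. It follows the percent summary, and 0.525 is larger than 0.514. The label is true on that reading, though the margin is 2% and the text does not name the comparison.

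The percent summary may be the relevant one. The two-week run-in was added after the pilot, and Section 4 keeps those who cannot provide data from being randomized. A denominator limited to weeks with data could also produce two means. Either is possible, but Section 12.2 makes neither argument.

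The count-based figures have limits. They rest on a six-week pilot SD and an unadjusted t-test, while the primary outcome averages weeks through Month 6 in a mixed model. The SD of the longer average may differ in either direction. The log-normal model also fits a 0 to 14 count poorly: with mean 5.5 and CV 0.87 it puts about 5% of values above 14, and it allows no zeros. The difference-scale figure is therefore the better one to report.

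A reader might infer that the true power is 48% to 51% and the stated 85% is wrong, or that the trial is too small. The documents support neither: they do not show that the count summary is the valid one, and the 84% calculation is unaffected.

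**Conclusion.** The point holds as an unreconciled inconsistency between inputs. On the stated denominator of 14, Section 12.2's two pilot summaries cannot both describe the primary weekly count, and the 85% is tied to the more favourable one.

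- **If the count summary applies:** power for a 1.25-fold change is about 48% on the difference scale (51% log-normal) at 91 per group, assuming the pilot SD of 4.8 carries over to the trial.
- **If the percent summary applies:** the 85% can stay.

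The conflict between the summaries and the arithmetic on each branch are certain. Which branch is right is not known from the documents. The choice also decides whether the 84% calculation refers to a 48% or a 30% gain. It should be fixed because it bears directly on how a null result would be read, but it does not undermine the enrolment target.

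**What to change.** Keep 244 dyads and the 84% calculation (2.65 episodes, SD 6.0). In Section 12.2:

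1. From the pilot data, state which summary matches the primary outcome and what its denominator is (for example, all weeks or only weeks with data).
2. Restate the 1.25-fold power for that mean and SD, on the difference scale to match the identity-link analysis. If 5.5 and 4.8 stand: about 48% for 1.375 episodes, with 80% power at about 2.0 episodes (1.36-fold). If 63% and 32% stand, the 85% can remain, with its ratio method named.
3. Until this is resolved, print both figures: 85% at CV 0.525, and about 48% to 51% at CV 0.87.
4. Say that the CV of 0.525 is larger than the percent CV of 0.514.
5. Say what 2.65 episodes means in relative terms: 48% on 5.5, or 30% on 8.8.

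The cost is a look at the pilot data and a rewording of one section. Sample size, outcome and analysis do not change. The downside is a possibly less favourable stated power.

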12.4 Final Analysis Plan

Intent-to-treat (ITT) analyses standard in incentive based behavioral economics studies will be utilized (e.g. Halpern *et al.* 2015, Patel *et al.* 2016). Generalized linear mixed models (GLMMs) will be used to compare primary and secondary outcomes over time between groups. GLMMs make fewer missing data assumptions than other methods, which assume missing data are missing completely at random. Identity link will be used for numeric (interval) outcomes (e.g., mean number of qualifying half-day toothbrushing episodes per week, through Month 6 visit; mean OHI-MIS plaque score; and TP pump weight change). The group x time interaction will also be assessed; short-term effects will be assessed for 1 month of the intervention, mid-term effects after the novelty effect of powered toothbrushing usually ends for the Month 3 Visit, and long-term effects for the Month 6 Visit (primary outcome), as well as, maintenance of behavior after removing the incentives for the Month 12 Visit. Recent, powerful Precision Medicine methods which do not inflate Type I error will be used to detect heterogeneity of treatment effects by groups of participants based on baseline characteristics (e.g., Lazar *et al.* 2013). Multiple imputation using chained equations (MICE) for arbitrary missingness patterns (Raghunathan *et al.* 2001; van Buuren 2007) will be used for sensitivity analyses. Supplemental analyses will also explore: a) trajectories of mean number of qualifying half-day brushing episodes per week over time; as well as b1) variability in morning brushing times, b2) variability in evening brushing times, and c) variability in weekday versus weekend brushing times associated with mean number of qualifying half-day brushing episodes, OHI-MIS plaque scores, and ASTDD BSS caries screening measures.

To examine potential impact of timing of drawing reward communication time, GLMM analyses as above will be performed comparing the weekly and quarterly drawing result communication arms for primary and secondary outcome data from Month 12 to Month 18.

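### The fold-change powers in section 12.2 (85%, 80%, 80%) fit a log-scale t-test, not the identity-link difference in means planned in 12.4

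*Combined protocol and SAP*

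**What the plan says.** Section 12.2 gives two sets of power figures for 91 per group. The first is on the raw scale: a difference of 2.65 episodes, common SD 6.0, 84% power.

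The second is supplementary and expressed as a ratio: "a sample size of 91 in each group was estimated to have 85% power to detect a 1.25-fold change in means (expected ratio"), "with the larger (more conservative) CV=0.525". The test is described only as "CV=0.525 using a two group 2-sided t-test with alpha=0.05", with no scale named. Two further cases follow, beginning "With a CV=0.567 and a 1.25-fold change" and ending "a CV=0.695 and a 1.30-fold change, n=91 per group is still estimated to have 80% power". The CV of 0.525 sits next to a pilot summary: "The mean percent of qualifying brushing episodes (out of 14 half-days per week) was 63% with a SD=32% for a CV=0.514".

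Section 3.2.1 bounds the outcome: "only one session per half-day window contributes to the weekly count, which can range from 0 to 14". Section 12.4 sets the analysis scale: "Identity link will be used for numeric (interval) outcomes (e.g., mean number of qualifying half-day toothbrushing episodes per week". The primary hypothesis in 12.1 is likewise a difference in mean episodes per week. No log transformation, log link or ratio analysis is planned for this outcome.

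**The concern.** A ratio of means combined with a CV is the usual input for a power calculation on log-normal data, where the test compares mean logarithms. If the printed powers came from that calculation, they describe a test the trial will not run. They appear in 12.2 to show that 91 per group keeps at least 80% power when the data are more variable. A reader or oversight body would take them as the power of the primary comparison for 1.25-fold and 1.30-fold effects.

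The bounded scale adds a second difficulty. With equal CVs the reward-arm SD must grow in proportion to its mean, while on a 0 to 14 scale the largest possible SD shrinks once the mean passes 7.

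**Working it through.** **Inputs.** From 12.2: 91 per group, two-sided alpha 0.05, and three cases (ratio R, CV, stated power): (1.25, 0.525, 85%), (1.25, 0.567, 80%), (1.30, 0.695, 80%). From 3.2.1: range 0 to 14. Power is from the noncentral t distribution with 180 degrees of freedom and noncentrality (effect/SD) × √(91/2).

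**Step 1. Design calculation.** 2.65/6.0 × √45.5 = 2.98, power 84.2%. This reproduces the stated 84% on the raw scale.

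**Step 2. The fold-change powers on three premises.**

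- Log scale, common CV: effect ln R, SD √ln(1+CV²). Case 1: 0.2231/0.4934 × √45.5 = 3.05.
- Identity scale, equal CV: in units of the control mean, effect R−1, SD CV × √((1+R²)/2). Case 1: 0.25/0.5943 × √45.5 = 2.84.
- Identity scale, common SD at CV × control mean: effect R−1, SD = CV. Case 1: 0.25/0.525 × √45.5 = 3.21.

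| Case (R, CV) | Stated | Log, common CV | Identity, equal CV | Identity, common SD |
|---|---|---|---|---|
| 1.25, 0.525 | 85% | 85.9% | 80.6% | 89.2% |
| 1.25, 0.567 | 80% | 80.9% | 74.3% | 84.1% |
| 1.30, 0.695 | 80% | 80.1% | 70.4% | 82.5% |

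Only the log-scale column fits all three. Setting the log SD equal to the CV does not (81.4%, 75.2%, 71.7%). As a check on the equal-CV column, 40,000 simulated trials per case with log-normal data and a raw-scale t-test gave 81.3%, 75.1% and 72.1%.

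**Step 3. Detectable ratios.** Solving the equal-CV identity formula for R at the stated powers (85%, 80%, 80%) gives about 1.27, 1.27 and 1.34, against the printed 1.25, 1.25 and 1.30.

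**Step 4. Feasibility on 0 to 14.** At mean m the largest possible SD is √(m(14−m)). Equal CV therefore requires a reward-arm mean of at most 14/(1+CV²), and a control mean of at most that value divided by R:

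- Case 1: 14/1.2756 = 10.98; divided by 1.25, 8.78.
- Case 2: 14/1.3215 = 10.59; divided by 1.25, 8.48.
- Case 3: 14/1.4830 = 9.44; divided by 1.30, 7.26.

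The 63% pilot figure is 0.63 × 14 = 8.82. As a control mean it exceeds the limit for case 1 by 0.04, for case 2 by 0.34 and for case 3 by 1.56. In case 3 the reward-arm mean would be 8.82 × 1.30 = 11.47 and the required SD 0.695 × 11.47 = 7.97, against a maximum of 5.39.

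With a common SD at 8.82, cases 1 and 2 are feasible (SD 4.63 and 5.00, against a maximum of 5.73 at mean 11.03). Case 3 is not (SD 6.13 against 5.39).

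At the other pilot mean in 12.2, 5.5, all three cases are feasible. The CV reported with that mean is 0.87, larger than any of the three.

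**The case against.** **The direction depends on an unstated premise.** Section 12.2 never says that the CV is equal across arms, and the one variance premise it names, in the first calculation, is a common SD. Under a common SD the identity-scale powers exceed the printed ones. This stands: a reader might infer from 81%, 74% and 70% that the planned analysis falls short of 80%, and the documents do not settle that. It does not rescue the printed figures. The premise that generates them is equal CV, and under the other premise they are still not the power of the planned test.

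**Feasibility.** A reader might also infer that none of the three cases can arise. That needs 8.82 to be exactly the control mean, and 12.2 presents 63% as pilot data without naming an arm. Case 1 is feasible up to 8.78, which is 62.7% of 14 and would also print as 63%. Case 2 is feasible up to 8.48. Only case 3 is clearly out of reach near 63%.

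**The t-test is not the planned model.** Section 12.4 plans a mixed model over time, so a two-sample t-test is an approximation on either scale. This is granted, but 12.2 uses the same approximation, and the scale mismatch remains.

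**No design consequence.** The paragraph is supplementary, and the 84% calculation stands on the correct scale. This is also granted. It limits the point to the supplementary figures.

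**Zero counts.** A dyad with a mean of 0 has no logarithm, but since no log analysis is planned this causes no problem in the analysis itself.

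**Conclusion.** The point holds for the supplementary powers. The printed 85%, 80% and 80% belong to a log-scale test with a common CV, while the plan tests a difference in means. For that difference the same inputs give 81%, 74% and 70% under equal CV, a shortfall of about 4, 6 and 10 points, or 89%, 84% and 83% under a common SD, about 4, 4 and 3 points above the printed values. Separately, the CV 0.695 case under equal CV cannot occur for control means above about 7.3. The other two cases are borderline near 8.82.

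This rests on three assumptions: that the log scale, which 12.2 does not name, was used (it is the only variant tried that reproduces all three figures); that a two-sample t-test approximates the planned model; and, for feasibility, the control mean.

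A reader might conclude that 91 per group is too few. The documents do not support that, because the raw-scale calculation for 2.65 episodes with SD 6.0 reproduces at 84.2% and matches the identity link.

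**What to change.** In 12.2, replace the fold-change powers with identity-scale figures and state the control mean and variance premise used. Under equal CV these are 81%, 74% and 70%, or equivalently detectable ratios of about 1.27, 1.27 and 1.34 for 85%, 80% and 80% power. Show the common-SD values (89%, 84%, 83%) as the other end of the range.

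Choose a control mean at which every retained case is feasible: under equal CV, no more than about 8.8, 8.5 and 7.3 for the three cases in turn. If the control mean is to be near 63% of 14, drop the CV 0.695 case. Keep the 2.65-episode, SD 6.0 calculation (84%) as the design power.

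The cost is a text edit. Some supplementary powers become less favourable. The sample size, enrolment target and analysis do not change.
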